4 STUDY MEASURES

4.1 Efficacy Measures

There are no efficacy measures in this study. IOP is assessed for safety.

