9 ADVERSE EVENTS

An Adverse Event (AE) is defined as any untoward and unintended medical occurrence (e.g., sign, symptom, disease, syndrome, intercurrent illness) that occurs in a study subject, regardless of the suspected cause during the study. Adverse events will be clearly documented on the study source document and monitored throughout the course of the study.

Events occurring after signing the informed consent but prior to the implant or procedure should be documented in the medical history. Events observed during or after the initial implant or exchange procedure until the final study visit, are to be recorded as AEs if they are in the study eye and deemed related to the implant or procedure.

Any clinically significant change in a subject's condition after receiving the study treatments, regardless of causality, is to be considered an adverse event, unless the change is determined to be a continuation of a pre-existing condition that is documented in the subject's medical history. If an adverse event occurs, an AE form must be completed.

An AE includes any of the following:

- An exacerbation or an unexpected increase in frequency or intensity of a pre-existing condition, including intermittent or episodic conditions
- New conditions or illnesses detected or diagnosed after the implant procedure
- A suspected interaction with any of the study treatments
- Signs, symptoms, or the clinical sequelae of a suspected overdose of either any of the study treatments or a concomitant medication
- Any clinically significant laboratory finding that was not present prior to receiving any of the study treatments

An AE does NOT include any of the following:

- Anticipated day-to-day fluctuations of any pre-existing conditions, including the disease under study (OAG and OHT).
- Medical or surgical procedure, (e.g., colonoscopy or hernia repair). The condition that led to the procedure may be an AE, if not present in medical history.
- Hospitalizations where an untoward medical occurrence did not occur (social or convenience admission to the hospital).
- Pre-existing conditions or diseases that were present before receiving any of the study treatments that do not worsen or that are chronic but stable
- Changes in a chronic condition or disease that are consistent with natural disease progression. (These medical conditions should be adequately documented).
- Lack of efficacy of the study treatment for the condition being investigated.

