## 4. General Statistical Considerations

Demographic and safety data collected on the case report forms (CRFs) will be displayed in tabulations and data listings. Only data from scheduled visits will be used in tabulations unless otherwise specified. No formal statistical testing will be performed. All data summaries and statistical analyses will be performed using SAS® software, Version 9.4 or higher.

Continuous data will be summarized using the number of observations, mean, standard deviation, median, minimum, and maximum. Continuous data may also be dichotomized, or otherwise split, into clinically meaningful categories and may be further analyzed as categorical data as specified in the individual endpoints.

Categorical data will be summarized using frequency counts and percentages. Unless otherwise stated, subjects with missing visit data will be omitted from both the numerator and denominator of such calculations.

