#### 7.1.3.10. Intraocular Pressure

IOP is assessed for safety and is measured at Screening and all postoperative visits. At Screening, IOP may be collected at any time of the day. At the remaining examinations, IOP must be measured at the same time as Screening  $\pm$  60 minutes.

The actual and change from baseline in IOP (mmHg) will be summarized by visit as a continuous variable. [REDACTED]

[REDACTED]

[REDACTED]

A subject listing presenting all IOP data will be provided.

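### Protocol Section 9 gives unreconciled rules on whether a clinically significant IOP rise after the exchange is an adverse event, so the same rise may be counted at one site and not at another

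*Protocol*

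**What the plan says.** The sole objective (Protocol Section 2) is the safety of the surgical exchange. On IOP, Protocol Section 4.1 states: "There are no efficacy measures in this study. IOP is assessed for safety". Section 8.4 repeats this, and SAP Sections 6.1 to 6.3 list no efficacy endpoint at any level.

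Protocol Section 9 contains statements that keep events out of the AE record:
- It excludes "Lack of efficacy of the study treatment for the condition being investigated".
- It excludes expected day-to-day fluctuation of pre-existing conditions, naming OAG and OHT, and changes consistent with natural disease progression.
- It has post-procedure events recorded if they are in the study eye and attributed to the implant or procedure.

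The same section contains statements that bring events in:
- "Any clinically significant change in a subject's condition after receiving the study treatments, regardless of causality, is to be considered an adverse event", with one exception: "unless the change is determined to be a continuation of a pre-existing condition that is documented in the subject's medical history".
- An AE includes "An exacerbation or an unexpected increase in frequency or intensity of a pre-existing condition".

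Outside the AE tables, SAP Section 7.1.3.10 says: "The actual and change from baseline in IOP (mmHg) will be summarized by visit as a continuous variable". It also provides a subject listing of all IOP data. SAP Section 4 defines the continuous summary as n, mean, SD, median, minimum and maximum, and adds: "Only data from scheduled visits will be used in tabulations unless otherwise specified". SAP Section 7.1.3 includes unscheduled visits in overall-study summaries.

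**The concern.** An exclusion for lack of efficacy makes sense where an efficacy endpoint picks up loss of effect. Here there is none. The product is an IOP-lowering implant and every subject has OAG or OHT, so inadequate IOP control is the natural meaning of lack of efficacy. The variable in question is nevertheless declared a safety measure.

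AE status also controls later outputs. Under Protocol Section 9.1 an event must be an adverse event before it can be a serious one. The TEAE tables, the severity tables, and the listings of SAEs and of AEs leading to implant removal in SAP Section 7.1.2 all draw on recorded AEs. An IOP rise that is labelled as something other than an AE reaches none of them. If sites label differently, the IOP-related event rate partly reflects labelling rather than the safety of the exchange.

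**Working it through.** The plan states no figure on this point. The sample size was set empirically and no testing is planned, so there is nothing to reproduce. The check is a comparison of the texts, followed by an illustration of scale.

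**Step 1: apply the Section 9 rules to one case.** Take a study-eye IOP rise after the exchange that the investigator considers clinically significant but whose cause is unclear.

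| Section 9 rule | Result |
|---|---|
| Clinically significant change, whatever the cause | AE |
| Exacerbation of a pre-existing condition | AE |
| Exception for continuation of a documented condition | Not an AE, if so judged |
| Fluctuation of OAG/OHT | Not an AE, if so judged |
| Natural progression | Not an AE, if so judged |
| Lack of efficacy | Not an AE, if so judged |
| Recording only if attributed to implant or procedure | Recorded only if judged related |

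No visible sentence ranks these rules or exempts IOP from the exclusions. Two investigators could classify the same reading differently and both cite Section 9.

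**Step 2: find the sharpest conflict.** The words "regardless of causality, is to be considered an adverse event" are about cause. Their direct opposite is the filter on attribution to the implant or procedure. The lack-of-efficacy bullet is a further route out of the AE record, alongside fluctuation and progression. Amending that bullet alone would leave the other routes open.

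**Step 3: see what remains outside the AE tables.** A rise at a scheduled visit enters the by-visit summary, where the maximum shows the largest value. A rise at an unscheduled visit appears, on the visible text, only in the listing: no overall-study IOP summary is visible for the unscheduled-visit rule to act on. No visible IOP output counts subjects with a rise.

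**Step 4: scale.** Inputs: n = 45, the approximate number in Protocol Section 6.1; the event counts and the size of the rise are assumptions.
- One omitted subject changes the AE proportion by 1/45 = 2.2 percentage points.
- Suppose three eyes rise by 15 mmHg at one scheduled visit and 42 do not change. Mean change = (3 × 15 + 42 × 0)/45 = 1.0 mmHg, median 0, maximum 15.
- Recorded as AEs, these are 3/45 = 6.7% (Clopper-Pearson 95% CI 1.4% to 18.3%).
- If none is recorded, the AE tables show 0/45 = 0% (95% CI 0% to 7.9%).
- For other counts: 1/45 = 2.2% (0.1% to 11.8%); 5/45 = 11.1% (3.7% to 24.1%).
- If the true rate of such events were 2%, 5% or 10%, the expected number of subjects would be 45 × 0.02 = 0.9, 45 × 0.05 = 2.25 or 45 × 0.10 = 4.5. The chance of at least one, 1 − (1 − p)^45, would be 60%, 90% or 99%.

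**The case against.** The strongest reply is that Section 9 already directs recording. Related study-eye events, clinically significant changes and exacerbations are all AEs, so a rise caused by the surgery is covered. A reader might infer that any post-exchange IOP rise, including a surgical one, can be dismissed as lack of efficacy. The documents do not support that: a rise produced by the operation is not a failure of the drug, and Section 9 has related study-eye events recorded. This part of the reply stands, and it confines the concern to rises of ambiguous cause.

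A reader might also infer that unrecorded rises vanish from the report. They do not. In the illustration the maximum change of +15 mmHg would stand next to the mean of +1.0, and with about 45 subjects the listing would identify all three eyes. This stands too. What is lost is the event, with its severity, relatedness and seriousness, and a tabulated count.

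Finally, much text is not shown: the visit procedures (Protocol Section 6.3), the content of Section 6.5 on IOP management, Appendix A, part of SAP Section 7.1.3.10 and SAP Section 11.1.2. A recording rule, a categorical IOP table or an overall-study summary may be there. Their absence cannot be asserted, so the point rests on the visible text of Section 9. Even if such a rule exists elsewhere, Section 9 should point to it.

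**Conclusion.** The visible text of Protocol Section 9 does not settle whether a clinically significant post-exchange IOP rise of ambiguous cause is an AE. Because IOP is only a safety measure here, inclusion in the AE, severity and serious-AE outputs can turn on the investigator's label. Each subject affected shifts the AE proportion by 2.2 percentage points at n = 45.

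This assumes that the enrolled number is close to 45 and that the unseen text holds no overriding rule. How many subjects would be affected cannot be derived from the documents; the counts above only show scale. The finding is an ambiguity that should be resolved, since it touches the trial's only objective. It is not a demonstrated loss of safety data.

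**What to change.** Reconcile the rules in Protocol Section 9 by adding one stand-alone sentence, for example: *Notwithstanding the exclusions listed in this section and the restriction to events attributed to the implant or procedure, a post-exchange IOP increase in the study eye that the investigator judges clinically significant is recorded as an AE whatever its presumed cause; its relationship to study treatment is graded separately.*

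The sentence has to prevail over the fluctuation, progression and lack-of-efficacy bullets, the exception for continuation of a documented condition, and the attribution filter. Otherwise it creates new contradictions. It fits the existing relatedness scale, which already has categories for unrelated events, and SAP Section 7.1.2, which tabulates related TEAEs separately. If redacted text already contains such a rule, replace the sentence with a cross-reference.

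The cost is one sentence in the protocol and matching CRF guidance. The IOP-related AE count may rise, including events later graded as unrelated. No IOP threshold or clinical management rule is proposed.

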9.1 Serious Adverse Event

Serious adverse events are defined as any findings that suggest a significant hazard, contraindication, side effect, or precaution. Any adverse event is considered a serious adverse event if it results in any of the following outcomes:

- Death
- Life- or sight-threatening
- Required admission to the hospital or prolongation of an existing hospitalization (emergency room visits that do not result in admission to the hospital should be evaluated for one of the other serious outcomes)
- A persistent or significant disability/incapacity
- A congenital anomaly/birth defect

The terms “mild,” “moderate,” and “severe” are measures of intensity; thus a severe AE is not necessarily serious. For example, nausea of several hours duration may be rated as severe, but may not be clinically serious.

Important medical events that may not result in death, be life-threatening, or require admission to the hospital may be considered a serious adverse drug experience when, based upon appropriate medical judgment, they may jeopardize the subject and may require medical or surgical intervention to prevent one of the outcomes listed above. A life-threatening event is any event that places the subject at substantial risk of death from the event as it occurred; it does not refer to an event that hypothetically might have caused death if it were more severe. A sight-threatening event is any event that places the subject at risk of permanently losing vision in either eye as a direct result of the event.

Serious adverse events must be reported to Glaukos immediately (preferably within 24 hours of knowledge of the event).

Email: [REDACTED]

When new significant information (including the outcome of the event) is obtained, the investigator should inform Glaukos as soon as possible. Depending on the nature of the AE, Glaukos may request copies of the ophthalmic and medical records of the subject. If the subject was hospitalized for a study-treatment related serious adverse event, a copy of the discharge summary must be forwarded to Glaukos as soon as possible.

9.2 Unexpected Adverse Event

An adverse event is considered “unexpected” if it is not listed in the investigator brochure or is not listed at the specificity or severity that has been observed, or is not consistent with the risk information described in the general investigational plan or protocol.

Unexpected adverse events must be reported to Glaukos immediately (preferably within 24 hours of knowledge of the event).

Email: [REDACTED]

When new significant information (including the outcome of the event) is obtained, the investigator should inform Glaukos as soon as possible. Depending on the nature of the AE, Glaukos may request copies of the ophthalmic and medical records of the subject. If the subject was hospitalized for a study-treatment related unexpected adverse event, a copy of the discharge summary must be forwarded to Glaukos as soon as possible.

9.3 Suspected, Unexpected, Serious, Adverse Reaction (SUSAR)

A Suspected, Unexpected, Serious, Adverse Reaction (SUSAR) is any AE for which there is evidence to suggest a causal relationship between the Travoprost Intraocular Implant and the AE, and which is assessed as both unexpected and serious. An unexpected adverse reaction, i.e. any untoward and unintended response to any of the study treatments, is one for which the nature and severity is inconsistent with the applicable reference safety information (e.g., Investigator's Brochure).

9.4 Adverse Events Follow-up

Adverse events will be followed and documented until the time of complete resolution, or resolution with sequelae, or exit from the study with an assessment of the outcome.

10 MAINTAINING THE MASK

Not applicable.

11 INFORMED CONSENT

The investigator or designee will discuss the purpose and pertinent details of the study with each subject. The Informed Consent Form must be approved by the governing Institutional Review Board (IRB) or Independent Ethics Committee (IEC). Prior to undergoing any study related change in their treatment or any study related procedures, a subject must understand, sign, and date the appropriate IRB-approved Informed Consent Form. The signed and dated Informed Consent Form will be retained with the study records, and a copy of the signed Informed Consent will be given to the subject.

12 INSTITUTIONAL REVIEW

This study must be reviewed and approved by an appropriate Institutional Review Board (IRB) or Independent Ethics Committee (IEC). A copy of the letter indicating IRB approval must be provided to Glaukos (or designee) prior to study initiation. Updates must be provided to the IRB by the investigator at least annually or as required by the IRB.

14 STATEMENT OF COMPLIANCE

This study will be conducted in compliance with the protocol, good clinical practices (GCP), and all applicable laws and regulations.

The clinical investigator must maintain all information supplied by Glaukos in confidence, and when this information is submitted to an institutional review board (IRB), independent ethics committee (IEC) or another group, it will be submitted with a designation that the material is confidential.

The clinical investigator must ensure that all persons assisting with the trial are adequately informed about the protocol, the investigational product(s), and their trial-related duties and functions.

15 RECORD KEEPING

15.1 Source Documents

The clinical investigator must maintain detailed source documents on all study subjects. Source documents include investigator subject study files, subject medical records, hospital charts, clinic charts, as well as the results of diagnostic tests (e.g., laboratory tests, visual field test printouts).

The following minimum information should be entered into the subject's medical record:

- The date the subject entered the study and the subject number
- The study protocol number and the name of Glaukos
- The date that informed consent was obtained
- Evidence that the subject meets study eligibility requirements (e.g., medical history, study procedures and/or evaluations)

- The dates of all study related subject visits
- Evidence that required procedures and/or evaluations were completed
- Use of any concurrent medications
- Documentation of study medication accountability, including a copy of study medication labels
- Occurrence and status of any adverse events
- The date the subject exited the study, and a notation as to whether the subject completed the study or was discontinued, including the reason for discontinuation

15.2 Data Collection

The clinical investigator must maintain detailed records on all enrolled subjects. Data for enrolled subjects will be collected with an electronic data capture system. The electronic database, which is Title 21 CFR Part 11 compliant, will be managed by a data management vendor. Access to the database will be granted to authorize study personnel based on their role after training; and the access will be password-protected. The data clarification process will be managed within the electronic data capture system by either system-generated or manually generated electronic queries. Accuracy of data will be verified by source data verification at regular intervals, and all corrections to data will be made in the database. CRF forms are completed for all enrolled subjects, regardless of their final study status (e.g., subject discontinuation, study termination).

15.3 Study Supply Accountability

15.4 Record Retention

[figure not shown]
All records relating to the conduct of this study are to be retained by the investigator until notified by Glaukos that the records may be destroyed.

The investigator will allow representatives of Glaukos' monitoring team (or designee), the governing institutional review board, the Food and Drug Administration (FDA), and other applicable regulatory agencies to inspect all study records, CRFs, and corresponding portions of the subject's office and/or hospital medical records at regular intervals throughout the study. These inspections are for the purpose of verifying adherence to the protocol, completeness, and exactness of the data being entered onto the CRF, and compliance with FDA or other regulatory agency regulations.

APPENDIX A: SCHEDULE OF VISITS AND MEASUREMENTS

APPENDIX B: OBLIGATIONS OF THE INVESTIGATOR

In summary, the clinical investigator has agreed to the following obligations:

- Obtaining informed consent from every subject prior to enrollment in the study and maintaining records of consent as part of the study records.
- Obtaining approval from the Institutional Review Board (IRB) before enrolling any subject; submitting verification of the approval to the Sponsor; submitting periodic progress reports (at least annually) and final report to IRB.
- Approving the protocol and conducting the study according to the protocol and applicable regulations; informing the Sponsor of all deviations from the protocol.
- Informing the IRB of all protocol amendments/modifications; sending the Sponsor a copy of the letter from the IRB approving the amendment/modification.
- Reporting to the Sponsor and the IRB any adverse experiences that occur in the course of the investigation.
- Keeping careful and accurate records of all clinical study data (study records must be considerably more exact and complete than those kept in ordinary medical practice); maintaining records of all materials submitted to the IRB and of all action by the IRB regarding the study.
- Making study records available for inspection by the Sponsor and representatives of the Food and Drug Administration and other applicable regulatory agencies; keeping records until notified by the Sponsor that they may be destroyed.
- Maintaining proper control and documentation of all test and control articles.
- Submitting the following records and reporting to the Sponsor (See I, II, and III).
 - I. Prior to Beginning the Study
 - A signed Form FDA-1572 or Statement of Investigator.
 - A current curriculum vitae (CV) if not submitted to Glaukos previously or if updated.
 - CVs for all sub-investigators listed on the 1572.
 - A letter from the Institutional Review Board (IRB) indicating that the protocol was approved, including the name and address of the IRB.
 - A copy of the consent form approved by IRB.
 - A list of current members of the IRB.

II. While the Study is in Progress

- Acknowledgment of receipt of the test and control articles; documentation of disposition of all test and control articles.
- Original Case Report Forms for each subject enrolled in the study.
- Information regarding all deviations from the protocol.
- Information regarding all adverse medical events occurring to a subject while enrolled in the study.
- Annual progress report (if study is ongoing for more than one year). Letter from the IRB indicating approval of the annual progress report.

III. Once the Study is Completed

- Disposition of all used and/or unused test and control articles, as well as documentation of all drug accountability.
- A final study report (if requested).
